#### **10.2.1.7 PAC-SYM**

For the PAC-SYM, each item is scored as 0=absence of symptom, 1=mild, 2=moderate, 3=severe, and 4=very severe. The 12 items of the PAC-SYM are assigned to 3 domains:

- Abdominal symptoms (items 1 to 4)
- Rectal symptoms (items 5 to 7)
- Stool symptoms (items 8 to 12).

The change from baseline in the total score and each construct score will be calculated for visits 3 and 4.

#### **10.2.1.8 PAC-QOL**

For the PAC-QOL, each of the 28 items is scored from 0 to 4. For items 18, 25, 26, 27, and 28, higher scores represent better outcomes. The scores for these items will be reversed (reversed score=4-original score), so that higher scores represent worse outcomes for all items. The 28-item PAC-QOL is divided into 4 subscales:

- Physical discomfort (items 1 to 4)
- Psychosocial discomfort (items 5 to 12)
- Worries/concerns (items 13 to 23)
- Satisfaction (items 24 to 28).

The change from baseline in the total score and each construct score will be calculated for visits 3 and 4.

#### **10.2.1.9 Additional Endpoints**

Additional endpoints to be calculated include:

- Doses of rescue laxatives required per week
- Number of enemas required per week
- Number of manual disimpaction procedures required per week

### **10.2.2 Calculation or derivation of feasibility variables**

The study population poses challenges in enrollment and study conduct. This is because most patients receiving daily opioid therapy that have advanced cancer may be medically compromised, have multiple co-morbidities, and burdened by the need for multiple medications. It may be difficult for such ill patients to participate in trials because of poor functional status, fatigue, and the need for frequent clinical visits.

This study will evaluate patient recruitment and retention in a test of an oral therapy requiring one dose per day—25 mg naloxegol. The inclusion criteria are broad and include patients with low

functional status and a short prognosis (2 months). The recruitment goal is to enter 1-2 eligible patients a month at each site into the study.

To evaluate feasibility, the number of patients entering the study per month at each site will be tracked. The retention rate, or the percentage of patients who complete the study, will be calculated for each study site. The goal is a retention rate of 80%. The percentage of screen failures and the percentage of withdrawals will also be calculated.

## **11.0 SAMPLE SIZE DETERMINATION AND STATISTICAL METHODS**

### **11.1 Determination of sample size**

This study has been designed to provide essential information about the potential viability and utility of a definitive adequately-powered superiority trial assessing the ability of naloxegol to provide better efficacy for OIC in cancer patients than current therapies. It is pilot trial with the primary aim of determining safety and tolerability of this drug in the medically ill cancer patient. A secondary aim is to determine whether an efficacy signal can be determined, and if so what the effect size is—information critical to the design of a larger trial. Finally, feasibility, as determined by the ability to recruit and conduct the study according to protocol, is another secondary aim.

As a pilot, sample size determination is not considered to be dispositive of the actual planned recruitment. The study has been planned to screen approximately 64 patients to obtain 44 randomly assigned patients—22 per group. Provided by an ██████████ statistician, this number per group would allow a detection of a group difference of  $0.58 \pm 90\%$  confidence interval at a 70% power and 10% type I error, using a 2 sided tests). This is based off of spontaneous bowel movements per week over 1-4 weeks in the Phase III study of naloxegol 25mg versus placebo in non-cancer patients.

### **11.2 Outcome analyses**

The analysis of the randomized dataset will evaluate an intent-to-treat (ITT) population, defined as all randomized patients participating. These analyses will be complemented by descriptive data from the open-label extension period.

#### **11.2.1 Safety and tolerability analyses**

Adverse events will be classified by body system and preferred team and summarized by the number of patients with events per treatment group. AEs which in the opinion of the investigator are unequivocally due to the progression of a patient's underlying cancer may be analyzed and tabulated separately from other AEs. The number of TEAEs related to the study drug or probably related to the study drug will be compared across active drug and placebo. The number of these AEs mapped to the GI tract will be additionally analyzed. As noted, this analysis will be augmented by descriptive incidence data from the extension period.

The change from baseline in the mean daily opioid dose and mean NRS pain scores (average and worst per day) will be summarized by treatment group, and tested within each treatment group using one-sample t-tests.

All laboratory test results, vital signs (sitting BP and pulse), ECG results, respiratory rate, hematology and blood chemistry will be summarized for each treatment group using descriptive statistics and change from baseline.

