### 6.3.1 Definition of adverse events

An adverse event is the development of an undesirable medical condition or the deterioration of a pre-existing medical condition following or during exposure to a pharmaceutical product, whether or not considered causally related to the product. An undesirable medical condition can be symptoms (eg, nausea, chest pain), signs (eg, tachycardia, enlarged liver) or the abnormal results of an investigation (eg, laboratory findings, electrocardiogram). In clinical studies, an AE can include an undesirable medical condition occurring at any time, including run-in or washout periods, even if no study treatment has been administered.

The term AE is used to include both serious and non-serious AEs.

Note: Although all AEs must be documented in the study participant's research files (as described below) only some AEs will be determined reportable to the IRB, based on the criteria listed above.

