### **Causality collection**

The investigator will assess causal relationship of each AE (ie, their relationship to study drug). Causality will be rated as “related”, “probably related”, “possibly related”, and “unrelated”.

For SAEs, causal relationship will also be assessed for other medication and study procedures. Note that for SAEs that could be associated with any study procedure, the causal relationship is implied as “yes.”

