# **10. EVALUATION AND CALCULATION OF VARIABLES**

## **10.1 Primary aims: tolerability and safety**

The primary aim of this pilot study is to assess the tolerability and safety of naloxegol 25 mg in the management of OIC in the cancer population. The secondary aims are to assess efficacy and feasibility. The primary endpoint for tolerability and safety will be the difference in AEs between study groups. The secondary endpoints for this aim will focus on pain-related variables.

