### **10.1.1 Adverse Events**

A treatment-emergent adverse event (TEAE) is defined as any AE that started on or after the first dose of study drug up to the last dose of study drug. An AE already present at the time of the first dose of study drug that worsens in intensity following exposure to study drug or an AE with an unknown/not reported onset date will also be considered as treatment-emergent. Adverse events occurring after the last dose of study drug will also be summarized, which among other purposes, may assess any potential withdrawal-type effects.

Time to onset of an AE (in days) will be calculated as:

$$\text{AE start date} - \text{Date of the first dose of study drug} + 1$$

Duration of an AE (in days) will be calculated as:

$$\text{AE resolution date} - \text{AE start date} + 1$$

AEs which in the opinion of the investigator are unequivocally due to cancer disease progression will be tabulated separately from all other AEs.

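### The primary safety endpoint is the between-arm difference in all AEs, but the only AE comparison planned is of TEAEs rated related or probably related

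*Combined protocol and SAP*

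**What the plan says.** Section 10.1 defines the endpoint: "The primary endpoint for tolerability and safety will be the difference in AEs between study groups". It sets no causality condition, and section 6.3.1 defines an AE as an event "whether or not considered causally related to the product".

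Section 11.2.1 describes the analysis. All AEs, classified by body system and preferred term, are to be "summarized by the number of patients with events per treatment group". One comparison follows: "The number of TEAEs related to the study drug or probably related to the study drug will be compared across active drug and placebo". Then, for GI events: "The number of these AEs mapped to the GI tract will be additionally analyzed". No test, effect measure or interval is named for any of these.

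The causality scale, under Causality collection in section 6.3.3, has four levels: "Causality will be rated as “related”, “probably related”, “possibly related”, and “unrelated".

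Cancer-progression events are treated in two places. Section 10.1.1 says "AEs which in the opinion of the investigator are unequivocally due to cancer disease progression will be tabulated separately from all other AEs". Section 11.2.1 says such events "may be analyzed and tabulated separately from other AEs".

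**The concern.** Tolerability and safety are the primary aim, so the comparison named in the analysis section should answer the endpoint named in section 10.1. It does not, for three reasons.

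- **Scope.** The comparison keeps two of the four causality levels. The endpoint keeps all four.
- **Unit.** The all-AE summary counts patients with events. The comparison, read literally, counts events, so at 22 per arm a patient with several events can weigh heavily.
- **GI events.** On the more natural reading, the word 'these' in the GI sentence points back to the related and probably related TEAEs, so the GI analysis carries the same filter.

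If this stands, the quantity that represents the primary endpoint (patients or events, filtered or not, progression events in or out) would be settled only once the data are available. The one comparison fixed in advance would depend on how investigators attribute each event. Attribution is hard in patients whom section 10.2.2 describes as having multiple co-morbidities and multiple medications.

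**Working it through.** **1. The text.** The plan gives no planning figure for AEs, so there is nothing of that kind to reproduce. The 22 per group in section 11.1 is based on spontaneous bowel movements per week and is taken here as given.

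| | Endpoint (10.1) | All-AE summary (11.2.1) | Comparison (11.2.1) |
|---|---|---|---|
| Causality | Any | Any | Related or probably related |
| Unit | Not stated | Patients with events | Number of TEAEs |
| Between-arm contrast | Yes, a difference | Not stated | Yes, method not named |

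No column gives a between-arm estimate of any-causality AEs.

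**2. Do the filtered and unfiltered comparisons estimate the same thing?** This is an illustration, and all rates in it are assumptions. Let any TEAE occur in 70% of naloxegol and 50% of placebo patients, a difference of 0.20.

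*Ratings carry no information.* The same fraction f of affected patients in each arm is rated related or probably related, so both rates are multiplied by f:
- f = 0.75: 0.525 − 0.375 = 0.15
- f = 0.50: 0.35 − 0.25 = 0.10
- f = 0.25: 0.175 − 0.125 = 0.05

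*Ratings are informative.* If drug-caused and background events are independent, the chance of a drug-caused event is 1 − 0.30/0.50 = 0.40. Let 5% of placebo patients be rated related or probably related, and let raters recognise a fraction c of drug-caused events. The filtered rate on naloxegol is 1 − 0.95 × (1 − 0.40c):
- c = 0.25: 0.145 − 0.05 = 0.095
- c = 0.50: 0.24 − 0.05 = 0.19
- c = 0.75: 0.335 − 0.05 = 0.285
- c = 1: 0.43 − 0.05 = 0.38

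Against an unfiltered 20 points, the filtered difference runs from 5 to 38 points.

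**3. Power.** With 22 per arm, exact enumeration of two binomials and an uncorrected chi-square test at two-sided 10%, the all-cause comparison has power 0.385. The filtered one has 0.259, 0.199 and 0.144 in the no-information cases, and 0.294, 0.604, 0.833 and 0.951 in the informative cases. It moves both ways.

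**4. Precision of an any-causality risk difference.** The Wald 90% half-width is 1.645 × √[(p₁q₁ + p₂q₂)/22], with q = 1 − p:
- 0.53 v 0.48: 1.645 × √(0.4987/22) = 0.248
- 0.50 v 0.50: 1.645 × √(0.50/22) = 0.248
- 0.70 v 0.50: 1.645 × √(0.46/22) = 0.238
- 0.80 v 0.70: 1.645 × √(0.37/22) = 0.213

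The first pair is the Phase II any-GI-AE rate in non-cancer patients (section 1.4). It bears on the GI comparison; the other pairs are assumed.

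**The case against.** The strongest reply is that this is a pilot with no safety decision rule, and that all AEs will be tabulated by arm as patients with events. With the randomized numbers known, anyone can compute the all-AE risk difference. That is true, and it limits the weight of the point. It does not make the named comparison match the named endpoint.

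A filter may also usefully remove background cancer events. That is a good reason to keep the filtered comparison as supportive.

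The GI sentence could refer to AEs in general, from the start of the paragraph. The restricted reading is the more natural one, but the sentence should be clarified rather than assumed.

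A reader might infer more than the documents support:

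- *That the filter biases the comparison between arms.* Tablets are identical in size and color (section 5.3.1) and sites are given only a bottle number (section 5.4.5), so attribution in the randomized period is made blind.
- *That the filter costs power.* Step 3 of the working shows that it can lower or raise it.
- *That open-label events would enter the comparison, because the TEAE window in section 10.1.1 runs to the last dose of study drug.* Sections 3.1, 11.2 and 11.2.1 already place the between-arm analysis in the randomized period and treat extension data as descriptive. Only the TEAE definition needs aligning.
- *That progression events must be counted in the main comparison.* Separate tabulation of events unequivocally due to progression is provided for in both sections and is a defensible choice. Only its wording, and its effect on the primary comparison, are unsettled.

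**Conclusion.** The concern holds as a mismatch between the endpoint and its analysis. Section 10.1 states an unfiltered difference in AEs; section 11.2.1 compares a causality-filtered count of events and names no between-arm estimate for the rest. This rests on the text alone.

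Its numerical size in this trial cannot be known from the documents. The 5 to 38 points against 20 depend on assumed event rates, an assumed 5% placebo rating rate and assumed rater behaviour. They show only that the two comparisons estimate different quantities. It is a modest specification fault, worth correcting because it concerns the primary endpoint and the correction is cheap.

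**What to change.** In section 11.2.1:

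1. Make the primary between-arm comparison the proportion of patients with at least one TEAE of any causality. Count onset or worsening from the first double-blind dose up to the first open-label dose. For patients who do not enter the extension, count to the end of the randomized-phase TEAE window. Include any extension of the randomized period of up to 3 days (sections 1.1 and 3.1.1), so do not impose a fixed 14-day cut-off. Align the TEAE definition in section 10.1.1 with this.
2. State the denominator, for example randomized patients who took at least one dose. Section 3.1.3 allows for randomized patients who take none.
3. Report the risk difference, naloxegol minus placebo, with a confidence interval, read as an estimate. A 90% level is a choice; the 10% error in section 11.1 refers to bowel movements.
4. Do the same for any GI TEAE.
5. Keep related and probably related TEAEs as a supportive comparison, counted by patient, and state where possibly related events belong.
6. Reconcile the mandatory wording of section 10.1.1 with the optional wording of section 11.2.1 on progression events, and state whether the primary comparison includes them. Showing it both ways is enough.

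The cost is a few sentences and two risk differences with intervals; the data are already collected. The downside is noise from background cancer events and a wide interval, about ±21 to ±25 points at 90% for assumed rates of 50% to 80% with all 22 per arm in the denominator. Where investigators recognise drug-caused events well, the supportive filtered comparison may be the more sensitive one. Patients who stop early still contribute a shorter window, which this change does not resolve.

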### **3. STUDY PLAN AND PROCEDURES**

#### **3.1 Overall study design and flow chart**

This is a multi-center phase IV study which has the evaluation of tolerability and safety as the primary aim and the evaluation of efficacy and feasibility as a secondary aim. It is a randomized, double-blind, placebo-controlled, two parallel arm clinical trial. Placebo will be used as a control to provide evidence of the balance of benefit and risks of a fixed dose of naloxegol 25 mg.

Patients will be recruited from a variety of settings, including outpatient oncology offices, palliative care clinics, and hospice and palliative care sites (home, assisted living facility, or inpatient hospice unit). Home visits are permitted for those subjects who are unable to attend a clinic visit.

Patients will be screened to determine whether they have opioid-treated cancer pain and constipation, and whether they have interest in learning more about the clinical trial. Patients who seek to proceed will provide written informed consent. Consenting patients will undergo pre-randomization study procedures, including a history and physical, a check of laboratory values, an electrocardiogram, and collection of baseline data. This eligibility confirmation/baseline period will last 7 days, after which the patient will be scheduled for the randomization visit if study criteria (including the stability of opioid regimen and constipation criteria) are met.

At the randomization visit, the patient will obtain study drug (naloxegol 25 mg or a placebo) and rescue laxative. Data collected during the 14-day double-blind, randomized, placebo-controlled period will be used to evaluate the tolerability, safety, feasibility, and efficacy of naloxegol 25 mg in the treatment of OIC in cancer patients.

Patients who complete the randomized portion of the study will be able to continue a 14-day open-label extension period, during which treatment will consist of a daily dose of 25 mg naloxegol. After this period, there will be a telephone follow-up at 7 days.

Figure 1

[figure not shown]

Table 1

14(60)

| Procedure/Scale   | Visit 1   | Visit 2                           | Visit 3                                      | Visit 4                            | Follow up  |
|---|---|-----------------------------------|--|------------------------------------|--|

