### **4.1 Inclusion criteria**

To be eligible for the study, patients must meet the following criteria:

- Men and women aged 18 or older: Women of child bearing potential must have a negative urine pregnancy test during the Screening/OIC Confirmation/Baseline period, a history of no sexual activity or consistent use of an effective birth control method for at least 12 weeks prior to the study, and agreement that no sexual activity or the method of birth control will be continued during the study and for a period of 8 weeks after it ends; male patients who are sexually active must agree to use a barrier method of contraception (condom with spermicide) from the first dose of IP until 12 weeks after their last dose
- Able to follow instructions in English, give informed consent and to answer patient reported outcomes (PRO) questions by himself/herself; the patient will provide written informed consent before initiation of any study-related procedures
- Active cancer of any type with an investigator-estimated life expectancy  $\geq$  8 weeks and a Palliative Performance Status scale score  $\geq$  30%
- Patients receiving concurrent chemotherapy must have received and recovered from a minimum of 1 cycle of the current chemotherapy regimen upon consenting to the study and be considered stable in the opinion of the investigator
- Chronic cancer-related pain, defined as pain for a minimum of  $\geq$ 2 weeks which on review by the investigator, can be attributed to the neoplasm or its treatment
- Daily treatment with an opioid drug which is taken at a dose equal to or greater than 20 mg morphine or its equivalent for at least one week, with no expectation of a decrease greater than 25% or an increase greater than 100% during the study period.
- Patients may or may not be on a stable laxative regimen, defined as daily use at a stable dose for  $\geq$ 7 days; if the patient is taking a stable dose, he or she must be willing to remain on that regimen for the 7 day confirmation period without titration or adjustments.

History of constipation, defined through history and through participation in the Screening/OIC Confirmation/Baseline period:

- Patient history must include 2 or more of the following during defecations occurring in the two weeks prior to screening:
  - <3 spontaneous bowel movements per week
  - hard/lumpy stools (Bristol Stool Scale Type 1 or 2) in more than 25% of defecations
  - sensation of incomplete evacuation in more than 25% of defecations

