### **Disease progression**

Disease progression can be considered as a worsening of a patient’s condition attributable to the disease for which the study drug is being studied, which in this study refers to the condition of

OIC. Adverse events, which are due to disease (ie, OIC) progression, in the opinion of the investigator, should not be reported as an AE, unless they meet SAE criteria.

Of note, patients in this study must have an opioid-requiring pain condition in order to participate. Any day-to-day type fluctuations in pain control common in this population should not be reported as AEs, unless they meet SAE criteria.

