### **6.3.5 Pain and opioid use**

The study drug is an opioid antagonist, and pain opioid use are therefore measured to determine whether the study drug may have an adverse effect on pain management

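### Pain scores and opioid dose are tested only within each arm, so the planned tests cannot show whether naloxegol worsens pain control relative to placebo

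*Combined protocol and SAP*

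**What the plan says.** Section 11.2.1 covers the change in average daily opioid dose and in the daily average and worst pain ratings. These "will be summarized by treatment group, and tested within each treatment group using one-sample t-tests". That is the only inference planned for these outcomes.

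The plan's purpose for them is comparative:

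- Section 6.3.5 notes that the drug is an opioid antagonist, and that pain and opioid use are therefore "measured to determine whether the study drug may have an adverse effect on pain management".
- Section 10.1, on the primary aim, says: "The secondary endpoints for this aim will focus on pain-related variables".
- Section 3.1 says: "Placebo will be used as a control to provide evidence of the balance of benefit and risks".

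Two other planned comparisons come close. Section 11.2.1 states: "The number of TEAEs related to the study drug or probably related to the study drug will be compared across active drug and placebo". Section 11.2.2 has a general sentence on t-tests between groups, but it follows a list of bowel and questionnaire outcomes that names neither pain nor opioid dose.

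**The concern.** A one-sample test asks whether an arm's mean change differs from zero. The stated question is whether the drug impairs pain control, and in a randomised trial the contrast with placebo answers that. If pain or opioid need shifts in both arms for other reasons, such as disease course or changes in analgesic care, a within-arm test picks up the shift and cannot separate it from a drug effect. Setting one significant p-value beside one non-significant p-value does not test the difference either.

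The error can go both ways. A common worsening can look like harm from naloxegol, and a common improvement can hide real harm. At stake is the trial's only quantitative evidence on whether an opioid antagonist affects analgesia in these patients.

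**Working it through.** **Is the contrast planned elsewhere?** No.

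- The list before the t-test sentence in 11.2.2 covers PAC-SYM, PAC-QOL, rescue laxative use, stool form, straining and evacuation.
- Opioid dose appears in 11.2.2 only as a possible modifier of bowel response and in a description of dose increases, not as a safety outcome compared between arms.
- The adverse event comparison does not substitute. The Disease progression paragraph of 6.3.3 says: "Any day-to-day type fluctuations in pain control common in this population should not be reported as AEs, unless they meet SAE criteria".

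**Inputs.**

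- From the documents: 22 per arm (11.1), 1:1 allocation (5.1.1), and a retention goal of 80% (10.2.2), so 0.8 × 22 = 17.6, or about 18 per arm.
- Not in the documents: the SD of the change scores, the drift common to both arms, and the significance level for these tests. Effects are therefore in SDs of the change score. I use a two-sided 5% level, with 10% (the type I error in 11.1 for bowel movements) alongside.
- Model assumptions: normal changes, equal SDs, independent arms. A rise is unfavourable for both pain and dose.

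The plan gives no figure for pain or opioid dose to reproduce. Its only sample size statement concerns bowel movements per week.

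**No drug effect, common drift d.** The one-sample test has a noncentral t distribution with 21 df and noncentrality d√22 = 4.690d. Call its rejection probability R(d), and the part in the unfavourable direction U(d). The pattern of naloxegol significantly worse and placebo not significant has probability U(d) × [1 − R(d)]. At d = 0.5 this is 0.609 × 0.391 = 0.238.

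| Drift (SD) | Naloxegol test rejects, 5% | Pattern, 5% | Naloxegol test rejects, 10% | Pattern, 10% |
|---|---|---|---|---|
| 0 | 0.050 | 0.024 | 0.100 | 0.045 |
| 0.1 | 0.073 | 0.060 | 0.135 | 0.101 |
| 0.2 | 0.146 | 0.123 | 0.236 | 0.176 |
| 0.3 | 0.269 | 0.196 | 0.390 | 0.237 |
| 0.5 | 0.609 | 0.238 | 0.734 | 0.195 |

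A between-arm t-test falsely indicates harm with probability 0.025 (5% level) or 0.050 (10% level) at every drift. With 18 per arm at 5%, the naloxegol test rejects 0.050, 0.069, 0.126, 0.225 and 0.516 of the time.

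**Real harm e, partly or fully offset by an improvement common to both arms (5% level, 22 per arm).** The between-arm test has 42 df and noncentrality e√(22/2) = 3.317e, whatever the offset.

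| Harm (SD) | Offset | Naloxegol within-arm | Placebo within-arm | Between-arm |
|---|---|---|---|---|
| 0.5 | none | 0.609 | 0.050 | 0.367 |
| 0.5 | half | 0.201 | 0.201 | 0.367 |
| 0.5 | full | 0.050 | 0.609 | 0.367 |
| 0.8 | none | 0.947 | 0.050 | 0.736 |
| 0.8 | half | 0.433 | 0.433 | 0.736 |
| 0.8 | full | 0.050 | 0.947 | 0.736 |

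**Two illustrative results, 22 per arm.** The within-arm t is the mean change × 4.690. The between-arm t is the difference ÷ √(2/22) = difference ÷ 0.3015.

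- Changes of +0.46 SD (naloxegol) and +0.38 SD (placebo): within-arm p = 0.043 and 0.089; between-arm t = 0.08 ÷ 0.3015 = 0.27, p = 0.79.
- Changes of +0.30 and −0.35 SD: within-arm p = 0.17 and 0.12; between-arm t = 0.65 ÷ 0.3015 = 2.16, p = 0.037.

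**Precision of the contrast.** The half-width is t(2n − 2) × √(2/n). With 22 per arm it is 0.507 SD (90%) or 0.608 SD (95%). With 18 per arm it is 0.564 SD or 0.677 SD.

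**The case against.** The strongest reply is that nothing is lost. The changes are summarised by arm, and if the tables give mean, SD and n, anyone can compute the unadjusted difference and its interval. That is true, and it limits the defect to the choice of prespecified inference. It does not make the planned p-values answer the stated question.

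Second, the error rates rest on assumed drift. Section 3.1 says that a patient "will be scheduled for the randomization visit if study criteria (including the stability of opioid regimen and constipation criteria) are met", and the double-blind period lasts only 14 days. With no drift there is no excess, and at 0.1 SD it is small. The plan also gives no rule for reading the two p-values together, so the pattern column describes how a reader might use them. These points stand. Drift is still not ruled out: section 4.1 requires only "no expectation of a decrease greater than 25% or an increase greater than 100% during the study period", which leaves more room for increases than for decreases, and section 5.5 permits changes to the opioid regimen.

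Third, full offset is a worst case, and with no offset the within-arm test is the more powerful (0.609 against 0.367 at 0.5 SD). This also stands: the gain is validity, not power.

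Fourth, sustained loss of analgesia or opioid withdrawal can still be recorded as an adverse event, so a between-arm comparison partly covers analgesic harm. It does not replace a contrast in measured pain or dose.

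Finally, dose changes may be skewed, so the normal-theory figures are approximate for that outcome.

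**Conclusion.** The concern holds and should be fixed. It rests on the text: sections 6.3.5, 10.1 and 3.1 pose a question about drug effect against placebo, while 11.2.1 tests change within each arm and no section supplies the contrast. The size is conditional. If both arms drift by 0.2 to 0.3 SD and the drug has no effect, the naloxegol test rejects 15% to 27% of the time at a nominal 5%, and the pattern of naloxegol worse with placebo not significant appears 12% to 20% of the time, against 2.5% for a between-arm test. With no drift the excess vanishes. These figures assume normal changes with equal SDs. The drift, the SD and the significance level are assumptions, not figures from the documents.

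These are secondary endpoints in a pilot, and the contrast will seldom settle the matter: its power is 37% for a harm of 0.5 SD and 74% for 0.8 SD. It does give an estimate of the right quantity with its uncertainty.

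**What to change.** In 11.2.1, make the naloxegol-minus-placebo difference the stated inference for opioid dose in morphine equivalents, average pain and worst pain. Define it as the difference in change from the OIC-confirmation baseline to the 14-day double-blind period, in the ITT population using available diary days, with a confidence interval and preferably adjusted for the baseline value. Keep the within-arm changes as description and drop their p-values.

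State the confidence level and that the three contrasts are for estimation. For opioid dose, add a check that is robust to skewness. Give the expected precision (90% half-width about 0.51 SD with 22 per arm and 0.56 SD with 18, before baseline adjustment), and say that a non-significant difference does not show that analgesia is preserved.

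The core change is about two sentences. It needs no new data, because sections 10.1.2 and 10.1.3 already derive the baselines, interval means and changes. No treatment or clinical rule is affected.
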